9.7.1.6 Efficacy Analyses

9.7.1.6.1 PRIMARY EFFICACY ANALYSIS

Primary analysis of ORR_{24W} will be based on a non-inferiority test. There will be two interim analyses and the primary analysis. The two interim analyses will be performed using only Per-Protocol Analysis Set 1. The primary analysis will be performed using the Per-Protocol Analysis Set 1 as the primary analysis set and will also be performed using Per-Protocol Analysis Set 2 and the Full Analysis Set as secondary analysis sets. At each interim analysis and primary analysis, the point estimate of ORR_{24W} for each treatment group (18 mg and 14 mg) will be summarized with the corresponding 95% confidence interval (CI). The odds ratio of ORR_{24W} (14 mg vs 18 mg) along with the 90% CI will be calculated using the Cochran-Mantel-Haenszel (CMH) method stratified by MSKCC prognostic groups and prior PD-1/PD-L1 treatment. Non-inferiority in ORR_{24W} will be claimed if the O'Brien-Fleming efficacy boundary is crossed at either interim analysis or primary analysis based on the results from the Per-Protocol Analysis Set 1. If the 1-sided P -value is ≤ 0.005 at the first interim analysis, or ≤ 0.014 at the second interim analysis, or ≤ 0.045 at the primary analysis, non-inferiority in ORR_{24W} will be claimed. Futility will be claimed if the futility boundary is crossed. If the 1-sided P -value is ≥ 0.776 at the first interim analysis, or ≥ 0.207 at the second interim analysis, futility will be claimed. The treatment difference in ORR_{24W} for 14 mg vs 18 mg will also be estimated along with 90% CIs based on the asymptotic normal approximation.

At each interim analysis and at the primary analysis, if the noninferiority boundary of the primary efficacy endpoint is crossed, the analysis of the primary safety analysis will be performed for Per-Protocol Safety Analysis Set. The primary safety endpoint is the proportion of subjects with intolerable Grade 2 or any \geq Grade 3 TEAEs within 24 weeks after randomization (as of the Week-24 time point). Frequency (number and percentage) will be summarized for intolerable Grade 2 or any \geq Grade 3 TEAEs within 24 weeks after randomization by treatment. The proportions will be tested using the CMH test (2-sided $\alpha=0.05$), stratified by MSKCC prognostic groups and prior PD-1/PD-L1 treatment. The proportions of the primary safety endpoint will also be summarized for Safety Analysis Set for descriptive purpose.

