Appendix 13 Efficacy and Futility Boundaries at Each Interim Analysis and the Primary Analysis

There will be 2 interim analyses and one primary analysis. The 2 interim analyses will be performed only in the Per-Protocol Analysis Set 1. The primary analysis will be performed in the Per-Protocol Analysis Set 1 as the primary analysis set, and will also be performed in the Per-Protocol Analysis Set 2 and in the Full Analysis Set as secondary analysis sets.

The tables below list the treatment differences in ORR_{24w} between the lenvatinib 14-mg + everolimus arm and the lenvatinib 18-mg + everolimus arm corresponding to the efficacy and futility boundaries at each interim analysis and primary analysis for different ORR_{24w} in the lenvatinib 18-mg + everolimus arm.

First interim analysis, non-inferiority stopping boundary OR = 1.788 (non-inferiority will be claimed if observed OR ≥ 1.788 at first interim analysis. Correspondingly, depending on ORR_{24w} , non-inferiority will be claimed if observed treatment difference between the 14-mg arm and the 18-mg arm is $\geq \delta$).

ORR_{24w} in lenvatinib 18-mg arm	δ = Treatment difference (lenvatinib 14-mg arm - lenvatinib 18-mg arm)
10%	0.07
20%	0.11
30%	0.13
40%	0.14
50%	0.14
60%	0.13

First interim analysis, futility stopping boundary OR = 0.590 (futility will be claimed if observed OR ≤ 0.590 at first interim analysis. Correspondingly, depending on ORR_{24w} , non-inferiority will be claimed if the observed treatment difference between 14-mg arm and 18-mg arm is $\leq \delta$)

ORR_{24w} in lenvatinib 18-mg arm	δ = Treatment difference (lenvatinib 14-mg arm - lenvatinib 18-mg arm)
10%	-0.04
20%	-0.07
30%	-0.10
40%	-0.12
50%	-0.13
60%	-0.13

Second interim analysis, non-inferiority stopping boundary OR = 1.436 (non-inferiority will be claimed if the observed OR ≥ 1.436 at second interim analysis. Correspondingly, depending on ORR_{24W}, non-inferiority will be claimed if the observed treatment difference between the 14-mg arm and the 18-mg arm is $\geq \delta$)

ORR _{24W} in lenvatinib 18-mg arm	δ = Treatment difference (lenvatinib 14-mg arm - lenvatinib 18-mg arm)
10%	0.04
20%	0.06
30%	0.08
40%	0.09
50%	0.09
60%	0.08

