Second interim analysis, futility stopping boundary OR = 0.962 (futility will be claimed if the observed OR ≤ 0.962 at the second interim analysis. Correspondingly, depending on ORR_{24W}, non-inferiority will be claimed if the observed treatment difference between the 14-mg arm and the 18-mg arm is $\leq \delta$)

ORR _{24W} in lenvatinib 18-mg arm	δ = Treatment difference (lenvatinib 14-mg arm - lenvatinib 18-mg arm)
10%	-0.003
20%	-0.006
30%	-0.008
40%	-0.009
50%	-0.010
60%	-0.009

Primary analysis, OR = 1.128 (non-inferiority will be claimed if observed OR ≥ 1.128 at the primary analysis. Correspondingly, depending on ORR_{24W}, non-inferiority will be claimed if the observed treatment difference between the 14-mg arm and the 18-mg arm is $\geq \delta$).

ORR _{24W} in lenvatinib 18-mg arm	δ = Treatment difference (lenvatinib 14-mg arm - lenvatinib 18-mg arm)
10%	0.01
20%	0.02
30%	0.03
40%	0.03
50%	0.03
60%	0.03

[figure not shown]
PROTOCOL SIGNATURE PAGE

Study Protocol Number: E7080-G000-218
Study Protocol Title: A Randomized, Open-Label (formerly Double-Blind), Phase 2 Trial to Assess Safety and Efficacy of Lenvatinib at Two Different Starting Doses (18 mg vs 14 mg QD) in Combination With Everolimus (5 mg QD) in Renal Cell Carcinoma Following One Prior VEGF-Targeted Treatment
Investigational Product Name: Lenvatinib (E7080), everolimus
IND Number: 124564
EudraCT Number: 2016-002778-11

SIGNATURES

Authors:

[figure not shown]
PPD

22 Sep 2020
Date

Oncology Business Group, Eisai Inc.

PPD

[figure not shown]

16 Sept. 2020
Date

PPD

Eisai Ltd.

PPD

Sep 15 / 2020
Date

Oncology Business Group, Eisai Inc.

INVESTIGATOR SIGNATURE PAGE

Study Protocol Number: E7080-G000-218

Study Protocol Title: A Randomized, Open-Label (formerly Double-Blind), Phase 2 Trial to Assess Safety and Efficacy of Lenvatinib at Two Different Starting Doses (18 mg vs 14 mg QD) in Combination With Everolimus (5 mg QD) in Renal Cell Carcinoma Following One Prior VEGF-Targeted Treatment

Investigational Product Name: Lenvatinib (E7080), everolimus

IND Number: 124564

EudraCT Number: 2016-002778-11

I have read this protocol and agree to conduct this study in accordance with all stipulations of the protocol and in accordance with International Council on Harmonisation of Technical Requirements for Registration of Pharmaceuticals for Human Use (ICH) and all applicable local Good Clinical Practice (GCP) guidelines, including the Declaration of Helsinki.

Medical Institution

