$$\exp((1-\delta) * (\text{upper limit of 95\% CI of log OR (everolimus/lenvatinib 18 mg + everolimus)})),$$

where $0 < \delta < 1$ is the retention rate.

To retain 70% of the lenvatinib 18 mg + everolimus vs. everolimus treatment effect, the non-inferiority margin (M) of the odds ratio is estimated to be:

$$M = \exp((1 - 0.7) * \log(0.395)) = 0.76 \text{ (i.e., } H_a: \text{OR (14 mg/18 mg)} > M \text{)}.$$

Table 1 below lists the non-inferiority margins on the scale of difference in ORR_{24W} between lenvatinib 14 mg + everolimus arm and lenvatinib 18 mg + everolimus arm corresponding to a 0.76 non-inferiority margin on the odds ratio scale for a different ORR_{24W} in lenvatinib 18 mg + everolimus arm.

Table 1 Non-inferiority Margins on Scale of Treatment Difference in ORR_{24W}

ORR _{24W} in lenvatinib 18 mg arm	Non-inferiority Margin on Difference Scale (lenvatinib 14 mg arm - lenvatinib 18 mg arm)
--	--

10%	-2%
20%	-4%
30%	-5%
40%	-6%
50%	-7%
60%	-7%

Two interim analyses will take place when 150 and 200 total subjects in the Per-Protocol Analysis Set 1 have completed 24 weeks follow-up or discontinue earlier. Each interim analysis will test both non-inferiority and futility of the 14 mg arm ORR_{24W} compared to the 18 mg arm ORR_{24W}. An O'Brien-Fleming stopping boundary will be used for non-inferiority. An interpolated non-binding stopping boundary will be used for futility, which will spend $\beta=0.005$ and $\beta=0.10$ at the first and second interim analysis, respectively. Assuming 37% ORR_{24W} in the lenvatinib 18 mg arm and 45% ORR_{24W} in the lenvatinib 14 mg arm, and adjusting for the interim analyses, a total of 306 subjects (153 per arm) in the Per-Protocol Analysis Set 1 is required to achieve 80% statistical power at 1-sided $\alpha=0.05$.

The stopping boundaries on the P value scale and the cumulative error probabilities spent at each interim analysis and final analysis are shown in Table 2 below. For example, at the second interim analysis, non-inferiority in ORR_{24W} will be claimed if the 1-sided P value is ≤ 0.014 ; futility will be claimed if the 1-sided P value is ≥ 0.207 .

Table 2 Stopping Boundaries

Analysis #	Cumulative α Spent	Efficacy Boundary (P value)	Cumulative β Spent	Futility Boundary (P value)
Interim Analysis #1	0.005	0.005	0.005	0.776
Interim Analysis #2	0.015	0.014	0.10	0.207
Final Analysis	0.05	0.045	0.2	0.045

SUPERIORITY OF PRIMARY SAFETY ENDPOINT COMPARING LENVATINIB 14 MG TO LENVATINIB 18 MG

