5.4.1 Primary Efficacy Analyses

The primary efficacy endpoint ORR_{24W} is defined as the proportion of subjects with BOR of CR or PR as of the Week 24 (after randomization) timepoint based on investigator assessments, during treatment or within 28 days after the last dose date but on or prior to the start of new anticancer therapy. Subjects with responses achieved after the start of new anticancer therapy or after 28 days from the last dose date will not be considered as responders.

The primary analysis of ORR_{24W} will be based on a non-inferiority test. The study hypothesis is that the ORR_{24W} for lenvatinib 14 mg QD in combination with everolimus 5 mg is non-inferior to the ORR_{24W} for lenvatinib 18 mg QD in combination with everolimus 5 mg in subjects with renal cell carcinoma following one prior VEGF-targeted treatment.

For this study, the non-inferiority of lenvatinib 14 mg QD in combination with everolimus 5 mg relative to lenvatinib 18 mg QD in combination with everolimus 5 mg is defined using 70% retention of the treatment effect of lenvatinib 18 mg QD in combination with everolimus vs. everolimus, which translated to the estimated odds ratio =0.76 for the non-inferiority margin following the approach of [Rothmann et al. \(2003\)](#).

The non-inferiority hypothesis for ORR_{24W} with the non-inferiority margin of odds ratio =0.76 for the final analysis can be stated as follows:

H_0 : Odds ratio of $ORR_{24W-14mg}$ vs $ORR_{24W-18mg} \leq 0.76$

H_a : Odds ratio of $ORR_{24W-14mg}$ vs $ORR_{24W-18mg} > 0.76$ (non-inferiority)

The primary analysis of ORR_{24W} will be performed on the Per-Protocol Analysis Set 1. The point estimate of ORR_{24W} with the corresponding 95% CI for each treatment arm will be summarized. The odds ratio of ORR_{24W} (lenvatinib 14 mg over lenvatinib 18 mg) along with the 90% CI will be calculated using the CMH method stratified by MSKCC prognostic group and prior PD-1/PD-L1 treatment. Non-inferiority in ORR_{24W} will be claimed if the O'Brien-Fleming efficacy boundary is crossed. If the 1-sided P value is ≤ 0.045 at the final analysis, non-inferiority in ORR_{24W} will be claimed (interim analysis is specified in [Section 6](#)). The boundary P value ≤ 0.045 for the final analysis is based on the plan that the two interim analyses will take place when the total number of 150 subjects and 200 subjects in the Per-Protocol Analysis Set 1 have completed 24 weeks of follow-up or discontinued early.

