13 APPENDICES

13.1 Efficacy and Futility Boundaries at Each Interim Analysis and Final Analysis

There will be 2 interim analyses and one final analysis. The 2 interim analyses will be performed only in the Per-Protocol Analysis Set 1 (based on investigator assessment). The final analysis will be performed in the Per-Protocol Analysis Set 1 as the primary analysis set, and will also be performed in the Per-Protocol Analysis Set 2 and in the Full Analysis Set as secondary analysis sets.

The tables below list the treatment differences in ORR_{24w} between lenvatinib 14 mg + everolimus arm and lenvatinib 18 mg + everolimus arm corresponding to the efficacy and futility boundaries at each interim analysis for different ORR_{24w} in lenvatinib 18 mg + everolimus arm.

First interim analysis, non-inferiority stopping boundary $OR=1.788$ (non-inferiority will be claimed if observed $OR \geq 1.788$ at first interim analysis. Correspondingly, depending on ORR_{24w} , non-inferiority will be claimed if observed treatment difference between lenvatinib 14 mg arm and lenvatinib 18 mg arm is $\geq \delta$).

ORR_{24w} in lenvatinib 18 mg arm	$\delta =$ Treatment difference (lenvatinib 14 mg arm - lenvatinib 18 mg arm)
10%	7%
20%	11%
30%	13%
40%	14%
50%	14%
60%	13%

First interim analysis, futility stopping boundary $OR=0.590$ (futility will be claimed if observed $OR \leq 0.590$ at first interim analysis. Correspondingly, depending on ORR_{24w} , futility will be claimed if the observed treatment difference between lenvatinib 14 mg arm and lenvatinib 18 mg arm is $\leq \delta$).

ORR _{24W} in lenvatinib 18 mg arm	δ = Treatment difference (lenvatinib 14 mg arm - lenvatinib 18 mg arm)
10%	-4%
20%	-7%
30%	-10%
40%	-12%
50%	-13%
60%	-13%

Second interim analysis, non-inferiority stopping boundary OR=1.436 (non-inferiority will be claimed if the observed OR ≥ 1.436 at second interim analysis. Correspondingly, depending on ORR_{24W}, non-inferiority will be claimed if the observed treatment difference between lenvatinib 14 mg arm and lenvatinib 8 mg arm is $\geq \delta$).

ORR _{24W} in lenvatinib 18 mg arm	δ = Treatment difference (lenvatinib 14 mg arm - lenvatinib 18 mg arm)
10%	4%
20%	6%
30%	8%
40%	9%
50%	9%
60%	8%

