Second interim analysis, futility stopping boundary OR=0.962 (futility will be claimed if the observed OR ≤ 0.962 at the second interim analysis. Correspondingly, depending on ORR_{24W}, futility will be claimed if the observed treatment difference between lenvatinib 14 mg arm and lenvatinib 18 mg arm is $\leq \delta$).

ORR _{24W} in lenvatinib 18 mg arm	δ = Treatment difference (lenvatinib 14 mg arm - lenvatinib 18 mg arm)
10%	-0.3%
20%	-0.6%
30%	-0.8%
40%	-0.9%
50%	-1.0%
60%	-0.9%

Final analysis, OR=1.128 (non-inferiority will be claimed if observed OR ≥ 1.128 at the final analysis. Correspondingly, depending on ORR_{24W}, non-inferiority will be claimed if the observed treatment difference between lenvatinib 14 mg arm and lenvatinib 18 mg arm is $\geq \delta$).

[figure not shown]

ORR _{24w} in lenvatinib 18 mg arm	δ = Treatment difference (lenvatinib 14 mg arm - lenvatinib 18 mg arm)
10%	1%
20%	2%
30%	3%
40%	3%
50%	3%
60%	3%

The above boundaries are based on the plan that the two interim analyses will take place when the total number of 150 subjects and 200 subjects in the Per-Protocol Analysis set 1 have completed 24 weeks of follow-up or discontinued early.

Safety and efficacy monitoring will be performed by an independent DMC. The function and membership of the DMC are described in the DMC charter. The recommendations concerning continuation or termination of the trial, or regarding modification of the trial or informed consent documents will be reached by the DMC based on the review of study safety and efficacy data. Determination of whether lenvatinib 14 mg can be used as an alternative dosing strategy will be based on clinical judgment by the Sponsor in consultation with the independent DMC (as specified in the DMC charter) by assessing risks and benefits according to the totality of data at either of the interim or final analyses.

The interim analyses together with the safety monitoring DMC analyses will be performed by an independent statistical reporting team, such as a statistical contract research organization.

SIGNATURE PAGE

Author:		
		Date
	Oncology Business Group, Eisai Inc.	
Approval:		
		Date
	Oncology Business Group, Eisai Inc.	
		
		Date
	Oncology Business Group, Eisai Ltd.

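### The appendices let non-inferiority be claimed at a fixed odds ratio or a rounded difference, which is not the same rule as P ≤ 0.045, and neither document says which governs

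*SAP*

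**What the plan says.** The bodies of both documents give one rule for the final look. SAP 5.4.1 sets a 1-sided P of at most 0.045, "at the final analysis, non-inferiority in ORR_{24W} will be claimed (interim analysis is specified in" Section 6); the null hypothesis is OR (14 mg over 18 mg) ≤ 0.76. Protocol 9.7.1.6.1 ties the claim to whether the O'Brien-Fleming "efficacy boundary is crossed at either interim analysis or primary analysis based on the results from the Per-Protocol Analysis Set 1", and gives the same P values. SAP 5.3.3 lists 0.005, 0.014 and 0.045 for the three looks and allows the superiority test on the primary safety endpoint only if non-inferiority is claimed.

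The appendices restate the claim in two other forms. SAP 13.1 has "Final analysis, OR=1.128 (non-inferiority will be claimed if observed OR" is at least 1.128, and then says it will also be claimed when the observed difference reaches a tabled value, in whole percents, for 18-mg rates from 10% to 60%. Protocol Appendix 13 matches: "Primary analysis, OR = 1.128 (non-inferiority will be claimed if observed OR" is at least 1.128.

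The only condition attached to the SAP 13.1 values is that the interims take place at 150 and 200 subjects. Neither appendix says that the OR values depend on the planning rates, or that the P value takes precedence.

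**The concern.** A fixed OR threshold equals a fixed P threshold only at one standard error, and the standard error depends on the response rates, the sample size, the arm split and the strata. The appendices nevertheless use one OR for 18-mg rates from 10% to 60%. Read as worded, one dataset can both meet and miss the primary claim.

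SAP 6 records that both interims were held in 2019, so the final analysis is the only look left. The claim made there opens or closes the primary safety test. In a borderline result, either conclusion could cite the SAP.

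**Working it through.** **Inputs.** Margin 0.76, P boundaries and planning rates of 37% (18 mg) and 45% (14 mg) from SAP 4, with "a total of 306 subjects (153 per arm) in the Per-Protocol Analysis Set 1 is required". The interims have 75 and 100 per arm (150 and 200 in total).

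**Reproducing the plan's values.** SE = √[1/(n·p₁(1−p₁)) + 1/(n·p₂(1−p₂))], and OR boundary = 0.76 × exp(z × SE). Lan-DeMets O'Brien-Fleming-type spending at information 150/306, 200/306 and 1 gives z = 2.568, 2.203 and 1.694.

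| Look | n per arm | SE at 37%/45% | OR boundary | Stated |
|---|---|---|---|---|
| Interim 1 | 75 | 0.3333 | 1.788 | 1.788 |
| Interim 2 | 100 | 0.2886 | 1.436 | 1.436 |
| Final | 153 | 0.2333 | 1.128 | 1.128 |

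The futility values of 0.590 and 0.962 reproduce from P = 0.776 and 0.207. The arithmetic is right, and it shows that the OR values carry the variance at 37%/45% and the planned N.

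**P when the observed OR is exactly 1.128.** With 153 per arm (unstratified Wald), z = ln(1.128/0.76)/SE = 0.3949/SE, where SE uses the observed rates.

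| 18-mg rate | 14-mg rate at OR 1.128 | SE | P |
|---|---|---|---|
| 20% | 22.0% | 0.281 | 0.080 |
| 25% | 27.3% | 0.260 | 0.065 |
| 30% | 32.6% | 0.247 | 0.055 |
| 37% | 39.9% | 0.235 | 0.047 |
| 40% | 42.9% | 0.232 | 0.045 |
| 50% | 53.0% | 0.229 | 0.042 |
| 60% | 62.9% | 0.235 | 0.046 |

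P equals 0.045 at 18-mg rates of 39.2% and 57.9%; outside that range an OR of 1.128 misses the P boundary.

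**Whole counts.** All responder pairs were enumerated.

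- 153 v 153: the OR and P rules can conflict at 46 or fewer 18-mg responders (30.1%) and at 103 or more (67.3%). From 47 to 102 they always agree.
- 152 (18 mg) v 154 (14 mg): conflicts run up to 53/152 (34.9%).
- 150 v 156: the conflict reverses at 61 to 63 of 150 (40.7–42.0%), where P passes and the OR fails.

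*Example 1.* 18 mg 46/153, 14 mg 50/153. OR = (50/103)/(46/107) = 1.129, so the OR rule claims. SE = √(1/46 + 1/107 + 1/50 + 1/103) = 0.2466, z = ln(1.129/0.76)/0.2466 = 1.606, P = 0.054, so the P rule does not. The difference is 4/153 = 2.6 points against the tabled 3 at 30%, so the difference rule does not claim either.

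*Example 2.* 18 mg 53/152, 14 mg 58/154. OR = (58/96)/(53/99) = 1.129, z = 1.661, P = 0.048. The OR rule claims and the P rule does not.

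**Type I error at the margin, final look taken alone.** True OR 0.76. The unstratified columns are exact binomial sums at 153 v 153. The documents give no strata sizes or stratum rates, so the stratified column is a range over 12 assumed settings (4 strata mixes by 3 levels of heterogeneity; Mantel-Haenszel OR with Robins-Breslow-Greenland SE; 306 subjects; 100,000 simulated trials per setting).

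| 18-mg rate | OR rule | P rule | OR rule, stratified |
|---|---|---|---|
| 37% | 4.9% | 4.6% | 5.0–5.9% |
| 30% | 6.4% | 4.8% | 6.3–7.1% |
| 25% | 7.3% | 4.2% | 7.5–8.3% |
| 20% | 9.5% | 4.1% | 9.3–10.0% |

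The stratified P rule stays at 4.3–4.6% throughout. With equal true rates, the two stratified rules disagree in 0.6–3.6% of trials at 37%, 3.8–6.3% at 30% and 6.9–8.9% at 25%. At the planned 37%/45% it is 0.1–2.3%.

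**Plausible rates.** The 37% comes from 19/51 in Study 205 (SAP 4), whose exact 95% CI is 24.1% to 51.9%.

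**The case against.** The strongest reply is that P is already the operative rule. It appears in the protocol synopsis and Protocol 9.7.1.6.1 and 9.7.2, and in SAP 4, 5.3.3, 5.4.1 and 6. SAP 5.3.3 presents the P values as the specific form of the boundary that controls type I error. The appendices read as a translation: the SAP 13.1 tables give differences "corresponding to the efficacy and futility boundaries at each interim analysis for different" 18-mg rates, and the specified analysis is a stratified CMH, so a statistician following SAP 5.4.1 would not look up a whole-percent table. Around 37% the rules almost always agree, the 20% rate lies outside the 24–52% interval, and the reversal at 150 v 156 turns on ORs of 1.124 to 1.127 against 1.128.

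Most of this stands, and it limits severity. It does not remove the contradiction. Both appendices state outright when the claim will be made, not merely what the boundary approximates. The SAP's lead sentence names only the interim analyses, although the section title and the protocol's version of that sentence also cover the last look. Observed 18-mg rates of 30% to 35%, where the two examples conflict, are well inside the interval.

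**Conclusion.** The concern holds. The tabled values are correct conversions at the planning assumptions, but they are worded as decision rules, they are not equivalent to P ≤ 0.045 at other rates, sample sizes or arm splits, and nothing ranks them below P. The effect is negligible near 37%. At 30% it raises single-look type I error from 4.8% to 6.4%, and more at lower rates. These figures rest on an unstratified Wald test with 153 per arm; the stratified ranges rest on assumed strata. Dose adoption rests on the totality of the data, so the exposure is to the formal claim and the safety test that depends on it. The point should be corrected before the final analysis.

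There are also clerical errors in the record of interims already held. In Protocol Appendix 13, the first futility block says that "non-inferiority will be claimed if the observed treatment difference between 14-mg arm and 18-mg arm is" at or below a negative value. The second futility block opens correctly ("Second interim analysis, futility stopping boundary OR = 0.962 (futility will be claimed if the observed OR" is at most 0.962) but its difference clause makes the same slip. The SAP says futility in both places. The second-interim non-inferiority row in SAP 13.1 names an 8 mg arm, while its table header says 18 mg. These slips carry no decision risk now.

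**What to change.** - State in SAP 13.1 and Protocol Appendix 13 that the stratified 1-sided P value for H0: OR ≤ 0.76 is the only decision rule.
- Label the OR and difference values as approximate conversions at 37%/45% and the planned N, not decision rules.
- Change non-inferiority to futility in the difference clauses of the two protocol futility blocks.
- Reconcile the 8 mg arm label in SAP 13.1 with its table header.

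The cost is one sentence and one label in each appendix plus three word corrections, with no new data, patients or analyses. The protocol edit needs a written amendment or administrative change under Protocol 11.1. If that has to wait, the SAP sentence can go in first, since Protocol 9.7 leaves analysis detail to the SAP.
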